### **2.2. Protocol Violations**

All protocol violations will be presented in a data listing.

### **3. GENERAL STATISTICAL METHODS**

#### **3.1. Sample Size Justification**

Approximately 50 subjects will be enrolled. The primary endpoint analysis will consist of a log-rank test of the difference in treatment groups in the time to viral clearance. Based on a recent publication

(<https://www.sciencedirect.com/science/article/pii/S2095809920300631?via%3Dihub>),

it is assumed that the median time to clearance for favipiravir would be approximately 4 days, and the median time for placebo would likely be approximately 11 days. This latter estimate may be conservative since SOC is not as likely to reduce viral load as well as the control in the above referenced study. Using two-sided alpha of 0.10 and power of 90% (appropriate for a trial to be used as the justification for a confirmatory, fully-powered, blinded and randomized Phase 3 study), and a fixed per-subject observation period of 15 days, an approximate sample size of 25 subjects per arm (total size of 50) is required.

#### **3.2. Efficacy Endpoints and Hypothesis Testing**

The primary efficacy endpoint is time to viral clearance by PCR, measured on Days 1, 3, 8, 11 (while hospitalized); and days 15 and 29 (if able to return to clinic or still hospitalized).

Contrary to what is included in the study protocol, the hierarchical testing of key secondary endpoints will not be performed. For more information please refer to [Section 5](#).

All analyses will be conducted at the two-sided alpha-level of 0.10. P-values for all analyses other than the primary efficacy endpoint will be presented for the purposes of ‘descriptive significance’ only.

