8 EFFICACY, PHARMACOKINETICS AND SAFETY ASSESSMENTS

8.1 Efficacy Assessments

Efficacy will be assessed by the following measurements:

- Presence of virus in the nasopharyngeal and oropharyngeal samples taken on Days 1, 3, 8, 11, 15 and 29 (if hospitalized and when able to return to clinic after discharge). Swabs will also be obtained on day of discharge from hospital if discharge occurs before Day 15.
- Clinical improvement of hospitalized subjects with COVID-19 receiving either favipiravir + SOC or SOC alone as defined by the following study-specific 6-point ordinal scale at Day 15

- 1. Not hospitalized
- 2. Hospitalized, not requiring supplemental oxygen
- 3. Hospitalized, requiring supplemental oxygen
- 4. Hospitalized, on non-invasive ventilation or high flow oxygen devices
- 5. Hospitalized, on invasive mechanical ventilation or ECMO
- 6. Death
- Status on the study specific 6-point ordinal scale assessed daily while hospitalized and at each outpatient visit until Day 60.
- NEWS2 assessed daily while hospitalized and at each outpatient visit until Day 60.
- Patient status assessed daily while hospitalized and at each outpatient visit until Day 60 via Study-specific Symptom Status and the ECOG Performance Status questionnaires (see Appendix A).
- Duration of supplemental oxygen (if applicable).
- Duration of mechanical ventilation (if applicable).
- Duration of hospitalization.
- Date and cause of death (if applicable).
- PCR and TCID50 in nasopharyngeal and oropharyngeal swabs on Days 1, 3, 8, 11, 15 and 29 (if hospitalized and when able to return to clinic after discharge), and on day of discharge if hospital discharge occurs before Day 15.
- Blood for determination of antibodies to SARS-CoV-2 obtained on Days 1, 15 and 29 (if hospitalized and when able to return to clinic after discharge).

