9.6 Efficacy Endpoint Analysis

The primary endpoint of time to viral clearance will be analyzed with the log-rank test for treatment difference and summarized using the Kaplan-Meier methodology as noted above. Viral load results from day of discharge as available will also be included in the analysis of viral clearance.

The key secondary endpoint of status of clinical recovery as measured by the study-specific 6-point ordinal scale at Day 15 will be analyzed using ordinal categorical data methods, since it is unlikely that linear differences exist between the elements of the scale (for example, a 1-point difference in magnitude may not apply to each increment on the scale). As an exploratory analysis, sequential binary analysis will be performed, based on successive classification of a subject into categories of less than or greater/equal to each ordinal item on the scale. Longitudinal analysis of the 6-point scale over time on study will also be performed to investigate temporal patterns of improvement.

Time to event endpoints will be analyzed using similar methods as used for the primary endpoint; these will include time to: clinical recovery; defervescence; cough mild or absent; dyspnea mild or absent; SARS-CoV-2 RT-PCR negative in upper respiratory tract.

Categorical endpoints will be analyzed using categorical data analysis methods; continuous data will be analyzed using analysis of variance with treatment and strata as factors.

Missing efficacy data in a trial of hospitalized patients is generally unlikely, and great care will be taken at each study site to ensure that all outcome assessments are obtained as planned in this protocol. However, as treatment of COVID-19 subjects evolves, it is clear some subjects will be discharged from the hospital prior to Day 15. Subjects are asked to return for follow up visits on Days 29, 45 and 60. This requirement is presenting challenges for subjects and in order to ensure that in cases where the subject does not return for their follow up visits, an additional swabbing has been added on the day of hospital discharge (See Section 7.7). Should missing data occur for the primary endpoint, time to viral clearance, such patients will be included in the log-rank analysis as censored observations. Missing clinical outcome data will be evaluated using a variety of methods, including multiple imputation, worst-value assignment, and other methods, to be completely outlined in the statistical analysis plan.

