### **4.3. Efficacy Evaluation**

#### **4.3.1. Analysis of the Primary Efficacy Endpoint**

The primary endpoint of time to viral clearance will be analyzed with the log-rank test for treatment difference based on a two-sided alpha-level of 0.10 and summarized using Kaplan-Meier methodology. The time to viral clearance (in days) is defined as the time of Negative or Lower Limit of Quantification (LLOQ) results (without any quantitative results after that) as measured by PCR for SARS-CoV-2 via scheduled nasopharyngeal and oropharyngeal swab samples minus the date of first dose + 1.

Subjects who have no evidence of viral clearance will be censored at the time of the last PCR measurement with the following conditions:

- Patients whose symptoms worsen (defined as an increase of  $\geq 1$  point on the 6-point Ordinal Scale from baseline) on the day of the last PCR measurement, or who die will be censored at Day 29,
- Patients who are lost to follow-up will be censored on the day of the last PCR measurement.

The median time to viral clearance will be estimated based on the Kaplan-Meier estimator; additional summary statistics will be presented, including the 25th and 75th percentiles, 90% CIs (the log-log transformation) on the median and other percentiles and proportion of censored subjects. Viral clearance rates at Days 3, 8, 11, 15, and 29 will also be presented.

The analysis of the primary efficacy endpoint will be done using the ITT population.

The primary analysis will be supplemented with a sensitivity analysis, using a stratified log-rank test, where the treatment difference based on a two-sided alpha-level of 0.10 will be summarized and stratified by disease severity.

The analysis will also be repeated by the dexamethasone usage subgroup, where patients will be categorized as having received dexamethasone if they received it at any time prior to the last viral clearance assessment.

Kaplan-Meier curves will be provided for the overall ITT population. By-subject data listings of viral clearance data will also be provided.

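### The SAP is inconsistent about which swabs define time to viral clearance: Section 3.2 limits Days 3, 8 and 11 to inpatients and names no discharge swab, and the narrowing is not declared

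*SAP*

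**What the plan says.** SAP 3.2 says that the PCR behind the primary endpoint is "measured on Days 1, 3, 8, 11 (while hospitalized); and days 15 and 29 (if able to return to clinic or still hospitalized". The two groups of days carry different conditions, and the discharge-day swab is not mentioned.

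SAP 4.3.1, which holds the event definition and censoring rules, measures clearance "via scheduled nasopharyngeal and oropharyngeal swab samples". It does not say whether the discharge swab is one of them, and it has no in-hospital limit.

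Other places are wider. Protocol 8.1 has "samples taken on Days 1, 3, 8, 11, 15 and 29 (if hospitalized and when able to return to clinic after discharge", plus a swab on the day of discharge when that falls before Day 15. Protocol 9.6 adds: "Viral load results from day of discharge as available will also be included in the analysis of viral clearance". SAP 1.2.6.1, under its primary-endpoint heading, lists all the swab days without an in-hospital limit and also lists the discharge swab. Note 11 to SAP Table 1-1 repeats the discharge swab.

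The protocol is not uniform either. Section 9.6 says "Subjects are asked to return for follow up visits on Days 29, 45 and 60", and the Section 13 schedule places Days 1 to 14 under a HOSPITALIZED heading. Yet 6.3.1 and 7.7 provide for subjects discharged before Day 14 who receive tablets to last until their next study visit.

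SAP Section 5 lists one change from the protocol, the removal of hierarchical testing.

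**The concern.** Time to viral clearance is the only endpoint whose p-value is not labelled descriptive (SAP 3.2), and Protocol 9.1 rests proof of concept on it. A programmer working from 3.2, from 1.2.6.1 or from 4.3.1 could assign different event dates to the same subject.

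The narrowest version, 3.2, makes inclusion of a result depend on whether the subject is still in hospital. Discharge happens after randomization, is decided by staff who know the treatment, and may differ by arm. If it does, the arms have different numbers of countable swabs in the first two weeks, which is where the planned difference lies. The choice should be closed before data are seen.

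**Working it through.** **1. The passages side by side**

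| Place | Days 3, 8, 11 after discharge | Discharge-day swab |
|---|---|---|
| Protocol 8.1 | Taken if subject can return | Taken |
| Protocol 9.6 | Return sentence names Days 29, 45, 60 only | Used in the analysis |
| SAP 1.2.6.1 | Listed, no in-hospital limit | Listed |
| SAP Table 1-1 | Column headed HOSPITALIZED | Note 11: taken |
| SAP 3.2 | In hospital only | Not named |
| SAP 4.3.1 | Scheduled swabs, no limit stated | Not stated |
| SAP 5 | No change declared | No change declared |

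**2. Effect on one subject.** Take a subject with a positive swab on Day 3, discharge on Day 5 with a positive discharge swab, and a negative outpatient swab on Day 8 that stays negative. Counting all protocol swabs, the event is at Day 8. Under 3.2 read literally it is at Day 15, or the subject is censored at Day 3 if they do not return on Day 15 or 29.

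**3. The plan's own sample size.** Inputs from SAP 3.1: "Using two-sided alpha of 0.10 and power of 90"%; "it is assumed that the median time to clearance for favipiravir would be approximately 4 days"; "the median time for placebo would likely be approximately 11 days"; 15 days of observation for each subject; 25 per arm. Exponential times are assumed here.
- P(event by Day 15): 1 − 2^(−15/4) = 0.926 and 1 − 2^(−15/11) = 0.611; mean 0.769.
- Hazard ratio 4/11 = 0.364.
- Freedman events: (1.645 + 1.282)² × (1.364/0.636)² = 39.3. Then 39.3/0.769 = 51.2, so 52 in total; power at 50 is 89.4%.
- Schoenfeld: 34 events, 45 subjects; power at 50 is 93.2%.

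The planned 50 therefore reproduces, but with every subject observed to Day 15 and no allowance for discharge.

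**4. Simulated power, medians 4 v 11 days, 25 per arm.** An event is the first negative swab with no later positive; otherwise the subject is censored at the last swab. The Day 29 rule for worsening or death was not modelled. Discharge timing and return rates are assumptions. The first six rows use 2000 runs each, log-normal discharge times and a clearance–discharge correlation of 0.5. The last two rows use full return with clearance and discharge independent, and their ranges span separate runs.

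| Median discharge, favipiravir v SOC | Return | SAP 3.2 literal | 3.2 plus discharge swab | All protocol swabs |
|---|---|---|---|---|
| Day 7 v 7 | 30% | 86% | 89% | 90% |
| Day 7 v 7 | 60% | 89% | 92% | 93% |
| Day 7 v 7 | 90% | 95% | 95% | 94% |
| Day 5 v 9 | 30% | 57% | 76% | 85% |
| Day 5 v 9 | 60% | 65% | 81% | 91% |
| Day 5 v 9 | 90% | 77% | 86% | 95% |
| Day 6 v 6 | 100% | 90–91% | – | 95% |
| Day 6 v 9 | 100% | 85–87% | 89–90% | 95% |

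Losses, all protocol swabs minus 3.2 literal: about 0–5 points with equal discharge; about 9 (95 − 86) for Day 6 v 9 with full return; 18 (95 − 77) to 28 (85 − 57) for Day 5 v 9 as return falls from 90% to 30%. Full return is an upper bound for the protocol schedule. With a 20% false-negative rate per swab, Day 5 v 9 gives 49–71% against 81–94%.

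**5. Simulated rejections with no true effect (nominal 5% each way)**

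| Scenario | Swab set | Against favipiravir | In favour |
|---|---|---|---|
| Day 6 v 9, full return, median clearance 7 days in both arms | 3.2 literal | 9.1–9.3% | 2.2–3.1% |
| Same | 3.2 plus discharge swab | 8.0% | 2.7% |
| Same | All protocol swabs | 5.0% | 5.2% |
| Day 5 v 9, 30–90% return, median clearance 11 days in both arms | 3.2 literal | 10.1–13.1% | 1.5–1.9% |
| Same | 3.2 plus discharge swab | 9.5–10.4% | 1.7–2.8% |
| Same | All protocol swabs | 5.0–7.1% | 3.5–5.2% |
| Day 7 v 7, 30–90% return, median clearance 11 days in both arms | 3.2 literal | 5.0–5.8% | 4.9–5.6% |

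The Monte Carlo standard error at 5% with 2000 runs is √(0.05 × 0.95/2000) = 0.5 points. Restoring the discharge swab alone leaves most of the asymmetry, so the in-hospital limit matters in its own right.

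**The case against.** The best defence is that 3.2 says when PCR is measured and gives no rule for discarding a result. Its wording follows the schedule headings. The operative definition is in 4.3.1, which has no in-hospital limit, and a swab required by the schedule's own note can fairly be called scheduled. This stands as a plausible reading, and it means that a reader who concludes that the SAP as a whole drops the discharge swab goes too far: 1.2.6.1 and Table 1-1 note 11 include it. It does not remove the conflict. Section 3.2 sets different conditions for the two groups of days within one sentence, and 4.3.1 does not settle which governs.

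A reader might also infer that earlier discharge will make favipiravir look slower. The documents do not support that as a general statement. It needs subjects discharged before a negative swab, and a difference in discharge timing between arms. Non-returners are censored, not dated late. A negative swab just before discharge also has fewer later swabs to overturn it, which works the other way, though it did not reverse the direction in the simulations. If SOC subjects left earlier, the bias would reverse.

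A third tempting inference is that discharged subjects are not asked back before Day 29. The Protocol 9.6 sentence also omits Day 15, so it is not a full visit list, and 6.3.1 and 7.7 presuppose earlier outpatient visits.

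Finally, the power figures depend on assumed inputs. With Day 6 v 9, full return and a clearance–discharge correlation of 0.5, literal 3.2 gives 89% power, and 92–93% with the discharge swab restored, close to the planned 90%. That is fair, and it is why the figures are illustrative.

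**Conclusion.** The inconsistency is established from the text. SAP 3.2 is narrower than SAP 1.2.6.1 and Protocol 8.1 and 9.6 on two counts, 4.3.1 does not resolve it, and Section 5 does not declare it. Followed literally, 3.2 would omit already planned swabs on a post-randomization condition, so it needs correcting before analysis.

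The size is conditional on 3.2 being what is programmed and on discharge and return patterns that the documents do not give. With equal discharge timing the loss is about 0–5 points of power with no directional bias. With earlier favipiravir discharge it is about 9 points under full return (Day 6 v 9) and larger under incomplete return (Day 5 v 9, 57–77% against 85–95%). The Day 5 v 9 runs differ from the Day 6 v 9 runs in discharge gap and correlation as well as in return. With no true effect, unequal discharge shifts rejections to roughly 8–13% against favipiravir and 2–3% in favour. None of this shows that the trial's result is biased.

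**What to change.** - In SAP 3.2, delete the in-hospital qualifier on Days 1, 3, 8 and 11.
- In SAP 3.2 and 4.3.1, state that every protocol swab result obtained counts at its actual date in both arms: Days 3, 8, 11, 15 and 29, inpatient or outpatient, plus the discharge-day swab. This matches SAP 1.2.6.1 and Protocol 8.1 and 9.6. If the narrower set is intended, declare and justify it in SAP Section 5.
- Tabulate swabs obtained by arm and visit. Even with all swabs counted, post-discharge results depend on the subject's ability to return, and Protocol 7.7 ties tablet refills to visits in the favipiravir arm only, so attendance may differ by arm.
- Reconcile the Protocol 9.6 return-visit sentence and the Section 13 HOSPITALIZED heading with Protocol 8.1.

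The cost is SAP wording, one table and a reconciliation of protocol text. Counting results already obtained needs no additional swabs or visits.

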#### **3.3. General Methods**

All data listings that contain an evaluation date will contain a relative study day (Rel Day). Pre-treatment and on-treatment study days are numbered relative to the day of the first dose of study medication which is designated as Day 1. The preceding day is Day -1, the day before that is Day -2, etc.

All output will be incorporated into Microsoft Word, or Adobe Acrobat PDF files, sorted and labeled according to the International Council for Harmonisation (ICH) recommendations, and formatted to the appropriate page size(s).

Tabulations will be produced for appropriate demographic, baseline, efficacy, PK, and safety parameters. For categorical variables, summary tabulations of the number and percentage of subjects within each category (with a category for missing data) of the parameter will be presented along with 2-sided 90% confidence intervals (CIs). For continuous variables, the number of subjects, mean, median, standard deviation (SD), minimum, and maximum values will be presented, as well as 2-sided 90% CIs. Time-to-event data will be summarized using Kaplan-Meier methodology using 25th, 50th (median), and 75th percentiles with associated 2-

sided 90% CIs, as well as percentage of censored observations. Where appropriate, p-values will be reported.

Assuming raw or derived variables are to 'x' decimal places, the data will be presented as follows:

- Range to x decimal places
- Mean and median to (x+1) decimal places
- SD to (x+2) decimal places
- (x+2) should not be greater than 4 decimal places
- percentages may be calculated without a decimal place or with (x+1) decimal place

Formal statistical hypothesis testing will be performed on the primary and secondary efficacy endpoints as described in [Section 4](#) with all tests conducted at the 2-sided, 0.10 level of significance.

Data will be presented by subject and summarized by treatment group.

### **3.4. Computing Environment**

All descriptive statistical analyses will be performed using SAS statistical software Version 9.4, unless otherwise noted. Medical history and adverse events will be coded using the Medical Dictionary for Regulatory Activities (MedDRA) Version 23.0. Concomitant medications will be coded using the WHO Drug Dictionary Version March 2020.

### **3.5. Baseline Definitions**

For all analyses, baseline will be defined as the most recent measurement prior to the first administration of study drug for patients on favipiravir. For patients on SOC, baseline will be defined as the closest (either before or after) measurement to randomization.

For the purpose of time-to-event analyses, treatment start date is used as the origin point for patients on favipiravir, while randomization date is used for patients on SOC.

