7.1 Day 1 (PRE-DOSE)

- Obtain informed consent.
- Verify eligibility per the inclusion and exclusion criteria. (See Sections 5.1 and 5.2)
 - o Review and record medical history, including tobacco use, to ensure there are no exclusionary illnesses.
 - Review and record concomitant medications for possible prohibited medications. (See Section 6.7)
- If subject is female of child-bearing potential and meets inclusion criteria 4.c, obtain urine or blood pregnancy test and proceed it result is negative.
- Measure and record vital signs (BP, HR, Temp, Resp).
 - **NOTE:** vital signs to be recorded and entered in the EDC every day while subject is in the hospital and on return study visits after discharge.
- Perform Physical exam (may be done by the Principal Investigator or their designee)
- Assess and record baseline clinical status according to the following study-specific 6-point scale:
 - 1. Not hospitalized
 - 2. Hospitalized, not requiring supplemental oxygen
 - 3. Hospitalized, requiring supplemental oxygen
 - 4. Hospitalized, on non-invasive ventilation or high flow oxygen devices
 - 5. Hospitalized, on invasive mechanical ventilation or ECMO

6. Death

NOTE: Clinical Status to be recorded and entered in the EDC every day while subject is in the hospital and on return study visits after discharge.

- Assess and record NEWS2 (See charts by clicking this link: https://www.rcplondon.ac.uk/projects/outputs/national-early-warning-score-news-2
 - **NOTE:** NEWS2 assessment to be recorded and entered in the EDC every day while subject is in the hospital and on return study visits after discharge.
- Assess and record ECOG Performance Status and Study-specific Symptom Status (see Appendix A).
 - **NOTE:** ECOG Performance Status and Study-specific Symptom Status to be collected and recorded every day while the subject is in the hospital and on return study visits after discharge.
- Collect nasopharyngeal and oropharyngeal swabs for virologic testing. (See Virology Laboratory Manual.)
- Collect blood samples for:
 - o Antibodies to SARS-CoV-2.
 - o Hematology and clinical chemistry laboratory analyses
- Collect and record SpO2 by Finger Sensor
 - **NOTE:** SpO2 to be recorded and entered in the EDC every day while subject is in the hospital and on return study visits after discharge.
- Perform subject randomization (via EDC) to establish treatment arm (favipiravir + SOC or SOC alone).

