- 11. Days 3, 8, 11 Nasopharyngeal and Oropharyngeal Swabs for Viral RNA, PCR and TCID₅₀ may be done +/- 1 day from their scheduled day. Swabs will also be obtained on day of discharge from hospital if discharge occurs before Day 15.
- 12. To be checked throughout hospitalization and at clinic visits and changes only recorded as applicable.

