| ECOG Performance
Status                               | X                 |   | X     | X     | X     | X      | X      | X                                       | X                  | X   |  |
| Study Specific
Symptom Status                         | X                 |   | X     | X     | X     | X      | X      | X                                       | X                  | X   |  |
| Randomization  | X                 |   |       |       |       |        |        |   |                    |   |  |
| Investigational Product
Dosing                                    |                   | Favipiravir Dosing Days 1-14
(1800mg BID on Day 1000mg BID Days 2-14)  |       |       |       |        |        |   |                    |   |  |
| Solicitation of
Treatment-Emergent
Adverse Events  |                   | X   | X     | X     | X     | X      | X      | X                                       | X                  | X   |  |
| Release from the Study   |                   |   |       |       |       |        |        |   |                    | X   |  |

1. Hematology, Chemistry (See Protocol Section 8.4).
2. May use results of labs taken at the hospital as part of SOC if done no more than 24 hours prior.
3. To be measured every day while hospitalized and at each clinic visit after hospital discharge through Day 60
  - a. Vital signs
  - b. Clinical Status 6-point scale
  - c. NEWS2
  - d. ECOG Performance status
  - e. Study-specific symptom status
  - f. Adverse Events
  - g. SpO2
  - h. Limited PE (heart and lungs)
4. PK on Day 1 prior to favipiravir dosing and between 45 to 75 minutes post-first dose.

5. PK trough samples to be taken approximately 30 minutes prior to any dose.
6. PK peak samples to be taken between 45 and 75 minutes post-dose.
7. Maintenance dose for CP score A is 800mg BID.
8. Days 45 and 60 may be completed in the hospital, outsubject clinic or by phone.
9. Subjects will undergo 9 planned venipunctures.
10. To be completed by PI or designee.
11. Days 3, 8, 11 Nasopharyngeal and Oropharyngeal Swabs for Viral RNA, PCR, and TCID50 may be done +/- 1 day from their scheduled day. Swabs will also be obtained on day of discharge from hospital if discharge occurs before Day 15.
12. To be checked throughout hospitalization and at clinic visits and changes only recorded as applicable.

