### **3.7. Adjustments for Covariates**

For the analyses of durations of supplemental oxygen, non-invasive/mechanical ventilation, Extracorporeal Membrane Oxygenation (ECMO), hospitalization, and ICU, baseline SpO2 level will act as a covariate in all analysis of covariance (ANCOVA) models. Disease severity, as defined in [Section 1.2.2](#), will be accounted for in all efficacy analyses. Other factors may be accounted for if deemed relevant.

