#### 4.3.2.9. Change in SARS-CoV-2 Viral Load

The change in SARS-CoV-2 viral load in upper respiratory tract specimen as assessed by area under viral load curve (quantitative PCR) as assessed up to 29 days. The area under the curve (AUC) over time for a given subject will be calculated, using the linear trapezoidal rule, as the sum of the maximum viral load for each day up through Day 29. Lower Limit of Quantification (LLOQ) result is considered as negative. An analysis of treatment group differences will be performed on the change in viral load using ANOVA model, with treatment group and disease severity as fixed factors.

The change in SARS-CoV-2 viral load will be analyzed by comparing the change between treatment groups using a mixed model with repeated measures (MMRM). This analysis will assess whether or not there is a difference in estimated change from baseline values between active treatment and SOC by visit using least squares means estimates from the MMRM. SAS PROC MIXED will be used to fit an MMRM with change from baseline in SARS-CoV-2 viral load as the response variable and the following covariates and fixed effects:

- Baseline SARS-CoV-2 viral load (covariate)
- Treatment group (fixed effect)
- Visit (fixed effect, time will be defined in terms of Visits)
- Time by Treatment Interaction (Time\*Treatment)

The covariance structure for the repeated measures in this model will be unstructured (UN). If UN does not converge for the model, a first-order autoregressive (AR(1)) covariance structure will be used.

Changes in viral load will be analyzed using the mITT population.

By-subject data listings will also be provided.

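### SAP 3.5 lets an SOC baseline fall after randomization but requires a favipiravir baseline before first dose, so some baselines may not be comparable between arms

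*SAP*

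**What the plan says.** SAP 3.5 applies the following to all analyses.

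- Favipiravir: "baseline will be defined as the most recent measurement prior to the first administration of study drug for patients on favipiravir".
- SOC: "For patients on SOC, baseline will be defined as the closest (either before or after) measurement to randomization". There is no limit on how late the value may be and no preference for the earlier of two.
- Time-to-event origin: "treatment start date is used as the origin point for patients on favipiravir, while randomization date is used for patients on SOC".

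Protocol 7.1 lists the Day 1 physical examination, vital signs, 6-point score, NEWS2, swabs, blood samples and SpO2 ahead of the randomization step. Protocol 7.2 and the schedule of assessments then repeat vital signs and SpO2 on Day 1 after dosing. The PK draw in the same list is limited to favipiravir subjects; these checks are not.

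The baseline value is used in several places:

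- SAP 3.7: baseline SpO2 "will act as a covariate in all analysis of covariance (ANCOVA) models" for the duration endpoints.
- SAP 4.3.2.9: the repeated-measures model takes "change from baseline in SARS-CoV-2 viral load as the response variable" and also adjusts for baseline viral load.
- SAP 4.3.2.4: change in NEWS2.
- SAP 4.3.2.1.1: the improved yes/no sensitivity analysis.
- SAP 4.5.3 and 4.5.4: laboratory shifts and vital-sign changes.
- SAP 4.3.1: the rule that censors an uncleared subject at Day 29 if the 6-point score has risen by at least one point from baseline.

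**The concern.** A baseline should be fixed before allocation can influence it, and by the same rule in both arms. Here an SOC value taken after randomization can serve as baseline. Whatever happened between randomization and that measurement then disappears from the SOC subject's change score. The same record in the favipiravir arm, with the later value taken after first dose, would count as follow-up. The trial is open label, so the later SOC value is also taken with allocation known.

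At stake are the comparability of the SpO2 covariate, of the change-from-baseline summaries and, in a narrow set of cases, of the Day 29 censoring rule.

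**Working it through.** **No plan figure depends on this.** The 25 per arm comes from medians of 4 and 11 days, two-sided alpha 0.10, 90% power and 15 days of observation. It reproduces closely: with HR = 4/11, Freedman events 39.3 divided by a mean event probability of 0.769 give 51.2 subjects, against 50. No baseline value enters it.

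**Step 1: where can a later SOC value be the closest?**

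| Measure | Next scheduled after Day 1 pre-dose | What makes an SOC baseline post-randomization |
|---|---|---|
| SpO2, vital signs | Day 1 post-dose | Repeat check nearer to randomization than the first |
| 6-point score, NEWS2 | Day 2, then daily in hospital | Day 1 value missing, or further away by the clock than the Day 2 value |
| Swabs | Day 3, which "may be done +/- 1 day from their scheduled day"; also at discharge | Day 1 swab missing, invalid or further away than the next swab |
| Laboratory | Day 3 | Day 1 value missing or further away; footnote 2 ("May use results of labs taken at the hospital as part of SOC if done no more than 24 hours prior") allows a result up to one day old, still normally nearer than Day 3 |

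SAP 3.5 does not say whether closeness is judged by clock time or by date. By date, Day 1 values tie and always beat Day 2. The only tie rule favouring the earlier value (SAP 3.11) is written for visit windows.

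**Step 2: a hypothetical record.** SpO2 at 09:00, randomization at 13:00, SpO2 again at 15:00. For an SOC subject the distances are 4 h and 2 h, so 15:00 is baseline. For a favipiravir subject dosed at 14:00, baseline stays at 09:00. However, a favipiravir reading at 13:30 would be that subject's baseline although it follows randomization.

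**Step 3: SpO2 covariate.** The adjusted difference is (Y_F − Y_S) − b(X_F − X_S), where Y is mean duration, X is mean baseline SpO2 and b is the common slope. If a share f of SOC baselines is late and SpO2 has moved by D on average in the interval, X_S moves by f·D. To first order the adjusted difference then moves by b·f·D. With b negative, D > 0 (early improvement) favours favipiravir and D < 0 favours SOC. The documents give none of b, f or D, so no figure can be attached.

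**Step 4: viral load, if Day 1 swabs are missing.** The offset in the between-arm difference in change is f × d × L, with d the natural decline per day and L the lag in days. All inputs are assumed: d = 0.1 to 0.3 log10/day, f = 10% to 100%, L = 0.5 to 3 days. The range is 0.1 × 0.10 × 0.5 = 0.005 to 0.3 × 1 × 3 = 0.9 log10. Simulated null trials (25 per arm, SD 1.5, correlation 0.6, d = 0.3, nominal alpha 0.10, 3,000 runs, one follow-up visit) gave:

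| f | L (days) | f × d × L | Type I error, change score | Type I error, baseline-adjusted |
|---|---|---|---|---|
| 10% | 0.5 | 0.015 | 0.096 | 0.093 |
| 25% | 2 | 0.15 | 0.128 | 0.111 |
| 50% | 2 | 0.30 | 0.200 | 0.146 |

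The baseline-adjusted column is nearer to the SAP model. Nothing in the documents suggests that 25% or 50% of Day 1 swabs would be missing, so the lower rows show sensitivity and are not a forecast.

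**Step 5: 6-point scale.** Suppose the pre-randomization score is b and a late baseline is b + 1. Improvement means y ≤ b − 1 against the first and y ≤ b against the second, so the class differs only at y = b. The worsening rule means y ≥ b + 1 against y ≥ b + 2, so it differs only at y = b + 1.

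**The case against.** The best defence is that the schedule already protects most measures. Baseline assessments precede randomization on Day 1. The 6-point score and NEWS2 are not due again until Day 2, nor swabs and laboratory tests until Day 3, so the Day 1 value is normally nearest. This stands, and it confines routine exposure to SpO2 and vital signs. Even there, Protocol 7.2 lists the repeat checks as following first dose; applying them to SOC subjects, who have no dose, is an inference.

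The analysis sets are also largely protected. TTCR, fever, cough, dyspnea and NEWS2 all admit subjects who qualify at baseline or study entry or within 72 hours, in both arms. P-values other than the primary are descriptive under SAP 3.2. Both points stand.

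Several stronger readings are tempting but unsupported:

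- That early change is removed from the control arm only. A favipiravir baseline can also follow randomization if it precedes first dose.
- That about half of SOC baselines, some 12 of 25, would be late. This assumes the nearest value is equally likely to fall before or after randomization, which the Day 1 ordering contradicts.
- That a one-point baseline shift turns a worsened subject into an improved one. Step 5 shows that no integer score does this.
- That the primary event times are distorted. They do not use the baseline value, which enters only through the Day 29 censoring rule for uncleared subjects.

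None of this removes the difference in the rule itself. Nothing elsewhere in either document restores a common definition.

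**Conclusion.** The point holds in a limited form. SAP 3.5 states non-equivalent baseline rules, and only the SOC rule lets baseline fall after that arm's own time zero. Under the planned schedule the exposure that can arise without missing data is mainly in SpO2 and vital signs, and its main efficacy use is the SpO2 covariate in the duration ANCOVAs. That assumes the Day 1 repeat checks are done in SOC subjects and that closeness is judged by clock time or same-date ties are left open. For the other measures the rule matters only when the Day 1 value is missing, invalid or further from randomization than the next one.

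The number affected is unknown, and the bias has no fixed direction: natural early improvement in SOC subjects favours favipiravir, and early worsening favours SOC. With few and short lags the effect is negligible. It becomes visible only with late-baseline shares that the documents give no reason to expect. The change is still worth making before analysis, because the option to use a later value adds nothing that a flagged fallback would not provide.

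**What to change.** In SAP 3.5, define baseline in both arms as the last measurement at or before randomization, and state whether this is judged by clock time or by date. Allow a later value (still before first dose for favipiravir) only where no earlier one exists. Flag such values, report their number by arm and by measure, and repeat the affected analyses without them as a sensitivity analysis.

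The cost is a sentence or two in the SAP and one derivation flag. Where Protocol 7.1 was followed, a pre-randomization value exists and no subject is lost. The one downside is that a few favipiravir baselines may be slightly older than the last pre-dose value.
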